11.2 Blood Pressure and Pulse

Blood pressure measurements will be taken using a mercury sphygmomanometer, a recently calibrated aneroid manometer, or a validated electronic device. Both systolic and diastolic blood pressure should be recorded. The first appearance of sound (phase 1) should be used to define systolic blood pressure and the disappearance of sound (phase 5) should be used to define diastolic blood pressure. Preferably, the same device should be used throughout the study and the same individual should record blood pressure throughout the study. An appropriate cuff size with a bladder encircling at least 80 percent of the arm should be used to ensure accurate measurement. Blood pressure should be measured in the sitting position after the patient has remained seated for at least 5 minutes, using the same arm at each visit.

Pulse measurements will be recorded using a full 60-second count while the patient is in the seated position.

Any clinically significant change in blood pressure or pulse measurements, in the investigator's judgment, compared to the screening values should be reported as an adverse event.

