7.1 Overall Study Design and Plan: Description

Study S0883 is a 42 day, multi-center, randomized, double-masked, active-controlled, parallel bioequivalence study of both eyes in subjects with primary open angle glaucoma or ocular hypertension who, following a washout of 4 to 28 days (depending on pre-study treatment) have an IOP ≥ 22 mmHg and ≤ 34 mmHg, ≤ 5 mmHg IOP difference between eyes and best corrected visual acuity (BCVA) better than or equal to 20/200 in each eye.

The screening visit will be conducted 4 to 42 days before the baseline visit (Day 1). All subjects must be washed out of topical or systemic ocular hypotensive medications prior to the baseline visit.

Table 1 Minimum Washout Periods for Ocular Hypotensive Medications

Medication	Minimum Washout Periods
Parasympathomimetics [eg, pilocarpine (Isopto® Carpine), carbachol (Isopto® Carbachol)]	4 days
Carbonic anhydrase inhibitors (systemic or topical) [eg, acetazolamide (Diamox®), dorzolamide hydrochloride (Trusopt®), brinzolamide (AZOPT®)]	4 days
Sympathomimetics [eg, dipivefron (Propine®), epinephrine (Epifrin®)]	2 weeks
Alpha-agonists [eg, apraclonidine (Iopidine®) brimonidine tartarate (Alphagan®, Alphagan® P), brimonidine and brinzolamide (Simbrinza®)]	2 weeks
Beta-adrenergic blocking agents [eg, timolol (Timoptic®, Betimol®, Timoptic XE®, Isatol®), timolol maleate and dorzolamide hydrochloride (Cosopt®), timolol maleate and brimonidine tartrate (Combigan®), levobunolol (Akbeta®, Betagan®), betaxolol (Betoptioc®, Betoptic-S®), metipranolol (Opti-Pranolol®), careteolol (Ocupress®)]	4 weeks
Prostaglandin analogs [eg, latanoprost (Xalatan®), travoprost (Travatan®), bimatoprost (Lumigan®), tafluprost (Zioptan™)]	4 weeks

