12. Use within one week prior to baseline of contact lenses.
13. Use within two weeks prior to baseline of: 1) topical ophthalmic corticosteroid; 2) topical corticosteroid; 3) systemic corticosteroid, or 4) high dose salicylate therapy (defined as stable daily doses exceeding 325 mg aspirin or equivalent)
14. Use within six months prior to baseline intravitreal or subtenon injection of ophthalmic corticosteroid.
15. Intraocular or refractive surgery (eg, cataract surgery, LASIK, etc.) within six months prior to Screening.
16. IOP lowering surgery (eg, Trabeculectomy, Laser trabeculoplasty, tube shunts, etc.) within 12 months prior to baseline.
17. History of severe dry eye in either eye.
18. Persons with Central Corneal Thickness (CCT) $>600\mu\text{m}$ in either eye.

19. Anticipate the need to initiate or modify medication (systemic or topical) that is known to affect IOP or blood pressure (eg, β -adrenergic antagonists, α -adrenergic agonists, calcium channel blockers, angiotensin-converting enzyme (ACE) inhibitors, and angiotensin II receptor blockers) during the study period.
20. Subjects with very narrow angles (3 quadrants with less than Grade 2 according to Shaffer's anterior chamber angle grading system) and subjects with angle closure, congenital, and secondary glaucoma, and subjects with history of angle closure in either eye.
21. Subjects with known or suspected drug or alcohol abuse.

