11.1 Schedule of Evaluations and Procedures

11.1.1 Screening Visit

Subjects will be screened from 4 to 42 days prior to administration of investigational product to confirm that they meet the subject selection criteria for the study. If the time between screening and dosing exceeds 6 weeks as a result of unexpected operational delays (eg, delayed drug shipment), then subjects do not require re-screening if at the baseline visit (Day 1) the patient meets the eligibility criteria.

The following procedures will be completed:

- Obtain informed consent;

- Obtain Subject Specific Identification
- Review inclusion/exclusion criteria;
- Collect demography;
- Complete medical history;
- Complete history of all prescription or nonprescription drugs, and dietary supplements taken within 30 days prior to signing the ICF;
- Blood pressure/pulse rate (sitting for 5 minutes);
- Visual field testing; if performed within 6 months (183 days) prior to screening and was documented in subject's records, no additional visual field testing is necessary
- Refraction
- Best corrected visual acuity;
- Collect Iris color: blue, brown, gray, green, hazel, or specify other;
- Biomicroscopy
- IOP
- Ophthalmoscopy
- Pachymetry
- Gonioscopy: (must use anesthesia): if performed within 6 months (183 days) prior to screening and was documented in subject's records, no additional screening gonioscopy examination is necessary
- Urine hCG for all females of childbearing potential;

If the subject meets the inclusion criteria:

- Discontinue topical and/or systemic ocular antihypertensives;

- Schedule the subject to return in 4 to 42 days (depending on washout time necessary for previous ocular hypotensive medication(s), Table 1, for the eligibility visit, Baseline (Day 1).
- Record any AEs that occur from the time the subject signs the ICF

To prepare for study participation, subjects will be instructed on use of Concomitant Medications ([Section 9.3](#)).

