11.1.2 Visit 1 (Day 1)

Subjects must continue to satisfy all inclusion/exclusion criteria in order to be eligible for randomization.

The following procedures will be completed:

- Re-check inclusion/exclusion criteria (only those eligibility criteria that apply at Day 1);
- Review prior/concomitant treatments;
- Blood pressure/pulse rate (sitting);
- Best corrected visual acuity;

NOTE: Refraction must be performed if a decrease in VA of two or more lines from the previous assessment occurs.

- Biomicroscopy
- IOP at 8:00 AM \pm 30 minutes and 10:00 AM \pm 30 minutes;
- Ophthalmoscopy
- Assess and record adverse events (AEs);
- Urine hCG for all females of childbearing potential;
- Randomize the subject to a treatment group;

- To prepare for study participation, subjects will be instructed on the use of Concomitant Medications ([Section 9.3](#));
- Dispense dosing diary and instruct subject on completion;
- Dispense investigational product in masked external packaging and instruct subject on self-administration, storage, and return.
- First dose will be self-administered at 4pm, then followed by 10pm dose.

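### Section 11.2 judges on-treatment blood pressure and pulse changes against screening values taken before washout, although a post-washout, pre-dose Day 1 value is already collected

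*Combined protocol and SAP*

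**What the plan says.** All references are to the combined protocol and SAP.

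- **The rule.** Section 11.2 covers "Any clinically significant change in blood pressure or pulse measurements, in the investigator's judgment", and such a change "compared to the screening values should be reported as an adverse event". It gives no numeric threshold and no other reference.
- **The screening measurement.** Section 11.1.1 includes "Blood pressure/pulse rate (sitting for 5 minutes" among the screening procedures. After the procedures, for subjects who meet the inclusion criteria, it says "Discontinue topical and/or systemic ocular antihypertensives".
- **Washout.** Section 7.1 states: "All subjects must be washed out of topical or systemic ocular hypotensive medications prior to the baseline visit". Table 1 sets minimum periods of 4 weeks for beta-blockers, 2 weeks for alpha-agonists, and 4 days for carbonic anhydrase inhibitors, a class that includes brinzolamide itself.
- **Relevance to BP.** Exclusion 19 in section 8.2 concerns systemic or topical medication "that is known to affect IOP or blood pressure". Beta-adrenergic antagonists and alpha-adrenergic agonists are among its examples.
- **The Day 1 measurement.** Section 11.1.2 repeats BP and pulse at Visit 1, after washout. The first dose follows at 4 PM that day.
- **AE definitions.** AEs are recorded from consent (11.1.1, 12.1.3). A treatment-emergent AE is one that starts on or after the first dose, or worsens after it (12.1.3).

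**The concern.** A safety reference should separate what happened before study drug from what happened on it. For a previously treated subject, the screening value does not: it is an on-drug value, and the protocol removes that drug before the first dose. Two misreadings become possible at Visits 2 to 4:

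- A change that washout alone produced can look like an on-treatment change.
- A real post-dose change that brings the subject back to the on-drug level can look like no change.

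BP and pulse are named safety measures in section 6.4, and comparing the safety of the two products is the only secondary objective (6.2). What is at stake is how clean that comparison is. AEs called by investigators at the visit cannot be reliably re-called later, so the reference is best fixed in advance.

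**Working it through.** No figure in the plan depends on this point, so there is none to reproduce. The check is on visit order and definitions.

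**Step 1: order of events for a previously treated subject**

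| Time | Event | Drug state |
|---|---|---|
| Screening | BP and pulse taken; then ocular hypotensives stopped | on prior drug |
| Between screening and Day 1 | washout (Table 1) | coming off |
| Visit 1, before 4 PM | BP and pulse taken; AEs assessed; randomization | washed out, undosed |
| Visits 2 to 4 | BP and pulse taken, judged against screening | on study drug |

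The comparison at Visits 2 to 4 therefore contains two changes: screening to Day 1 (washout) and Day 1 to the visit (study drug, plus natural variation). Only the second bears on the products.

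**Step 2: age of the reference**

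Screening is 4 to 42 days before Day 1. Visit 4 on Day 42 is 41 days after Day 1. At Visit 4 the screening reference is 4 + 41 = 45 to 42 + 41 = 83 days old, against 41 days for a Day 1 reference (nominal visit day, before the ±4-day window). Section 11.1.1 also waives re-screening after operational delays, so the gap can exceed 42 days.

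**Step 3: how a washout change is classified**

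- Called at Visit 1: it starts before the first dose and is not treatment-emergent unless it worsens.
- First called at Visit 2 or later: its start date falls after the first dose, so it meets the treatment-emergent definition.

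**Step 4: direction of the effect (illustration only)**

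Every input here is an assumption, and the numeric flag stands in for a judgment that the protocol leaves open. Take a pulse flag at an absolute change of T = 15 bpm or more, an SD of the between-visit difference s of 6 to 10 bpm, a washout rise w of 3 to 8 bpm, and a drug effect e of 0 or -10 bpm. With Φ the standard normal distribution function,

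P(flag) = 1 - Φ((T - m)/s) + Φ((-T - m)/s),

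where m = w + e against screening and m = e against Day 1.

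Example with s = 8, w = 5:

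- e = 0, screening: m = 5, so 1 - Φ(1.25) + Φ(-2.5) = 0.112. Day 1: m = 0, giving 0.061.
- e = -10, screening: m = -5, giving 0.112. Day 1: m = -10, so 1 - Φ(3.125) + Φ(-0.625) = 0.267.

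| Case (an affected subject) | Against screening | Against Day 1 |
|---|---|---|
| No drug effect | 2.4% to 25.3% | 1.2% to 13.4% |
| True fall of 10 bpm | 1.7% to 22.6% | 20.2% to 31.5% |

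With w = 0 the two references give identical results, so the gap comes from the washout shift alone. The figures show direction; they do not estimate this trial.

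**Step 5: effect on the between-arm difference**

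Washout is finished before 1:1 randomization, so extra events should arise at the same rate b in both arms. If they arise independently of true events, each arm's observed rate is p + b(1 - p), and the difference is (p1 - p0)(1 - b). If the same fraction k of true events goes unflagged in both arms, the difference is multiplied by (1 - k). Either way a true difference shrinks toward zero, and no difference appears where none exists.

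**The case against.** The strongest defence has five parts.

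1. **The rule is filtered by judgment.** A reader might infer that a former beta-blocker user whose pulse rose during washout meets the rule at every visit. The text does not support that. The change must be judged clinically significant, the investigator knows the washout history, and a persisting change is one ongoing event. This stands: such a subject *can* meet the rule. Judgment still needs a reference, however, and section 11.2 supplies the pre-washout one.
2. **Other reporting routes remain open.** A reader might infer that real drug effects will be hidden. Section 12.1.1 requires all observed AEs, section 12.1.3 covers any unfavorable sign after consent without reference to screening, and the visit-level values allow change from Day 1 to be calculated. This largely stands. What remains is that the specific BP and pulse trigger can miss a change back toward screening.
3. **Visit 1 already separates many washout changes** from treatment-emergent ones. This stands for changes called at that visit, not for those first called later. That section 13.3 does not expressly limit its tiered tables to treatment-emergent events is a separate gap.
4. **Screening is a coherent convention.** It matches AE recording from consent, and section 11.4 uses it for visual acuity. This is fair, and it explains the choice. It does not make screening the better reference for on-treatment changes when a drug has been withdrawn in between.
5. **The mechanism is only partly documented.** Exclusion 19 refers to IOP *or* BP, does not say which class affects which, and mentions no pulse effect. This stands, so any figure for pulse is an assumption.

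**Conclusion.** The point holds in limited form. For subjects on ocular hypotensives at screening, section 11.2 sets an on-drug reference and passes over the post-washout, pre-dose value taken at Visit 1. Washout changes first called at Visit 2 or later can become treatment-emergent AEs, and some post-dose changes need not trigger the rule.

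The size cannot be derived. The documents give neither the share of subjects coming off a relevant drug nor the shift this causes, and subjects untreated at screening are not affected. The conclusion assumes that stopping at least some of these drugs moves BP or pulse. Exclusion 19 makes that plausible for BP without establishing it class by class.

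Two stronger readings should be resisted. One is that the safety comparison is biased toward one product: washout precedes masked 1:1 randomization, so the expected result is noise and dilution in both arms alike. The other is that section 13.3 analyses BP and pulse from the wrong baseline: it names no baseline, and section 13 leaves detailed methods to an SAP, so no error there can be shown. The primary IOP analysis is unaffected. This is a modest improvement that is cheap enough to be worth making.

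**What to change.** In section 11.2, make the Visit 1 (Day 1) pre-dose BP and pulse the reference for judging changes at all visits after the first dose. Keep the screening values as the reference for changes found at Visit 1, which are pre-treatment AEs.

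No new measurement is needed. Section 11.1.2 describes the Day 1 reading only as "Blood pressure/pulse rate (sitting", without the five minutes stated at the other visits, but section 11.2 already requires at least five minutes seated for BP, so the readings are comparable if that is followed.

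The cost is one sentence of protocol text and a BP and pulse reference that differs from the screening reference used for visual acuity in section 11.4. Sites would need to be told of that difference.

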11.3 Visual Fields

Perform visual fields assessments following the study site's standard practices. If a visual field assessment was performed within 6 months (183 days) prior to screening and is documented in subject's records, no additional screening visual field examination is necessary.

11.4 Best Corrected Visual Acuity

Preferably, the same visual acuity examiner should perform each best corrected visual acuity measurement for a given subject. Best corrected visual acuity (BCVA) will be assessed using an Early Treatment Diabetic Retinopathy Study (ETDRS) eye chart (placed at 13 feet or 4 meters) or equivalent eye chart. BCVA should be performed prior to any exam requiring contact with the eye or drops to dilate or anesthetize the eye. If most of the letters are read on a line, then that line will be counted. For example, if the patient reads 20/25 +3, 20/20 will be recorded. Only the nearest Snellen line will be reported without plus and minus letters.

A decrease in BCVA of 3 lines or more from the screening visit will be reported as an adverse event. If visual acuity at screening is better than 20/20, any decrease in visual acuity will be calculated from 20/20.

The BCVA will be assessed at all visits as indicated in the Schedule of Activities.

11.5 Refraction

At the screening visit, the manifest refraction will be measured and recorded. The sphere will be noted, cylinder and axis of the refraction will be recorded. Plano will be recorded as 0.00 as it applies to the sphere and/or cylinder. Refraction must be performed at subsequent visits (1, 2, 3 and/or 4) only if a decrease in visual acuity (VA) of two or more lines from the previous assessment occurs. If refraction must be re-measured due to a decrease in BCVA from the previous assessment, the BCVA should also be repeated using the updated refraction values.

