*: Refraction to be performed if there was a two line decrease in BCVA from the previous assessment
Table 2 above, should be followed in order as schedule of assessments

8 Subject Selection

The following eligibility criteria are designed to select subjects for whom participation in the study is considered appropriate. All relevant medical and nonmedical conditions should be

taken into consideration when deciding whether a particular subject is suitable for this protocol.

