11.1.3 Visit 2 (Day 14)

The following procedures will be completed on Day 14 \pm 4 days:

- Review concomitant treatments;
- Check dosing diary;
- Blood pressure/pulse rate (sitting for 5 minutes);
- Best corrected visual acuity;

NOTE: Refraction must be performed if a decrease in VA of two or more lines from the previous assessment occurs.

- Biomicroscopy;
- IOP at \pm 30 minutes of 8:00 AM (prior to 8:00 AM dose of investigational product) and 10:00 AM. The 8:00 AM dose must be self-administered within 30 minutes of 8:00 AM in a secluded room without any investigational site staff present.
Investigational site staff must not be in the room whenever the treatment is taken out of the masked external packaging or the subject is dosed with investigational product. Subject knowledge and understanding of the dosing requirements must be verified before the subject leaves the investigator site at each visit
- Ophthalmoscopy
- Assess and record AEs.

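### A BCVA-loss adverse event can be reached one line at a time with no repeat refraction required on the way

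*Combined protocol and SAP*

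**What the plan says.** Section 11.5 schedules one refraction for every subject: "At the screening visit, the manifest refraction will be measured and recorded". At Visits 1 to 4 refraction must be done "only if a decrease in visual acuity (VA) of two or more lines from the previous assessment occurs". When it is re-measured for that reason, "the BCVA should also be repeated using the updated refraction values".

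The visit notes in Sections 11.1.2 to 11.1.5 carry the same trigger, for example "Refraction must be performed if a decrease in VA of two or more lines from the previous assessment occurs" at Day 14. So does the footnote to Table 2 in Section 7.1: "Refraction to be performed if there was a two line decrease in BCVA from the previous assessment". In Table 2 the footnote mark also covers the Early Termination visit.

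Section 11.4 sets the safety rule: "A decrease in BCVA of 3 lines or more from the screening visit will be reported as an adverse event". It adds a floor: "If visual acuity at screening is better than 20/20, any decrease in visual acuity will be calculated from 20/20". On resolution it says: "Only the nearest Snellen line will be reported without plus and minus letters".

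No section requires refraction for a cumulative loss from screening, or before a BCVA loss is reported as an adverse event.

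**The concern.** The two rules look back to different visits. The refraction rule asks what has happened since the last assessment; the adverse event rule asks what has happened since screening. A loss that builds up one line at a time is invisible to the first rule and accumulates under the second.

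BCVA and refraction are both named safety measures (Sections 6.4 and 13.3). Section 11.5 treats a new refraction followed by a repeat BCVA as the way to check an apparent fall in acuity. It requires that check for a 2-line fall between visits, but not for a 3-line cumulative fall that is reported as an adverse event. In that case the value recorded as best corrected may rest on the screening refraction, and a change in refraction may be reported as a loss of best corrected acuity.

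**Working it through.** The plan gives no figure on this point, so there is none to reproduce. The check is a count of the loss sequences that satisfy one rule and not the other.

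**Inputs**
- BCVA is assessed at screening and at Visits 1, 2, 3 and 4 (Table 2), which gives four steps. An Early Termination visit replaces a later visit and adds no fifth step.
- Acuity is recorded in whole lines (Section 11.4).
- Refraction trigger: a fall of 2 or more lines in one step (Section 11.5).
- Adverse event: a fall of 3 or more lines from screening, or from 20/20 if screening was better (Section 11.4).
- Assumption: both rules are applied to one eye at a time.

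**Screening acuity 20/20 or worse**

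Let d1 to d4 be the lines lost at Visits 1 to 4. No required refraction means every d is at most 1. The adverse event means d1 + … + dk ≥ 3 at some visit k ≤ 4. With steps of at most 1, this needs three one-line losses and at most one step with no change. A one-line gain rules it out, because 1 + 1 + 1 − 1 = 2. The sequences are:

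| Lines lost at Visits 1, 2, 3, 4 | Adverse event rule met at |
|---|---|
| 1, 1, 1 | Visit 3 |
| 0, 1, 1, 1 | Visit 4 |
| 1, 0, 1, 1 | Visit 4 |
| 1, 1, 0, 1 | Visit 4 |

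A full enumeration of losses of 0 to 3 lines per step gives the same four. An example of the first row is 20/20 → 20/25 → 20/32 → 20/40, which is an adverse event at Visit 3 on the screening refraction.

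**Screening acuity better than 20/20, trigger read as the raw visit-to-visit fall**
- One line better: the raw loss must reach 1 + 3 = 4 lines, so only 1, 1, 1, 1 remains, at Visit 4.
- Two lines better: the raw loss must reach 2 + 3 = 5 lines, more than four one-line steps allow. No sequence remains.

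Section 11.4 does not make clear whether the 20/20 floor also governs the refraction trigger. If it does, untriggered sequences exist in both cases. For a subject screened one line better, a raw loss of 2, 1, 1 counts as 1, 1, 1. For a subject screened two lines better, a raw loss of 3, 1, 1 counts as 1, 1, 1.

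**Mixed sequences (screening 20/20 or worse)**

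Any single fall of 2 or more lines does trigger refraction. With 1 line then 2, refraction falls at the adverse event visit. With 2 lines then 1, it falls at the earlier visit and is not required again when the adverse event threshold is crossed.

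**After the fix**

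If refraction is also required whenever the loss reaches the adverse event threshold, the sequences that reach the event with no required refraction fall from 4 to 0.

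**The case against.** The strongest reply is that two references serve two purposes: a visit-to-visit measurement check and a cumulative safety flag. They do not contradict each other. That stands, and the point here is a gap between the rules, not an inconsistency. Several stronger readings are tempting, and the documents do not support them.

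- **That the acuity is never re-corrected.** The visit notes say when refraction must be done and do not forbid it at other times. The word *only* in Section 11.5 can be read more strictly, but need not be. The supportable statement is that re-refraction is not required.
- **That the record cannot separate true visual loss from refractive change.** Section 12.1.1 obliges the investigator to obtain enough information to determine the outcome and causality of every adverse event, and Section 12.3 requires a causality assessment. Neither names refraction, but the work-up may include it. The cornea is also examined directly by biomicroscopy at every visit (Table 2, Section 11.7).
- **That the gap falls on the pattern a slow corneal effect would produce.** Section 5.2 of the label in Appendix A notes a potential for corneal edema in patients with low endothelial cell counts and gives no time course.
- **That a refractive shift after stopping a miotic shows the mechanism.** Such a shift would fall mainly between screening and Visit 1. At 2 or more lines it triggers refraction at Visit 1. At 1 line it needs two further one-line losses to reach the threshold.
- **That a 4-line loss could pass unexamined.** Where three of the lines are lost by Visit 3, the event is already reportable there (screening 20/20 or worse) and follow-up under Section 12.1.1 applies before Visit 4.

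The objection also notes correctly that no event is hidden: the loss is reported with or without refraction. The likely error is over-reporting of refractive change. What remains is that no section requires the check Section 11.5 already prescribes for smaller, faster losses.

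**Conclusion.** The gap is real and minor. One-line losses at three visits meet the adverse event rule at Visit 3 or Visit 4 with no required re-refraction or repeat BCVA. There are four such sequences when screening acuity is 20/20 or worse. If screening is one line better than 20/20 there is one, and if two lines better none, provided the trigger is the raw visit-to-visit fall.

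The effect is on the classification of individual safety findings. It applies equally to both masked arms and leaves the IOP endpoint untouched. The documents give no rates of acuity change, so the number of subjects affected cannot be estimated. This is an inexpensive improvement and not a threat to the trial's conclusions.

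**What to change.** In Section 11.5, the visit notes in Sections 11.1.2 to 11.1.5 and the Table 2 footnote, keep the existing trigger and add a second: refraction with repeat BCVA is also required when the loss reaches the Section 11.4 adverse event threshold, that is, 3 or more lines from screening, counted from 20/20 if screening was better. In Section 11.4, state that the adverse event rule is applied to the repeated BCVA.

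Tying the second trigger to the 3-line threshold and its floor is preferable to 2 lines from screening. The latter would fire more often than needed, including at every later visit for a stable 2-line loss. Without the floor, it would also call for refraction in a subject screened two lines better than 20/20 who later reads 20/20, where Section 11.4 counts no decrease.

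The cost is a few words in each place and a small number of extra refractions, using a procedure already in the protocol.
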